9.5.2.4. Safety Laboratory Results

Descriptive statistics will be provided for the clinical laboratory results (blood chemistry, hematology, coagulation, urinalysis, urine protein, Ig, lymphocyte subsets, and vaccine titers) by scheduled time of evaluation and by treatment group, as well as for the change from baseline. In addition, mean change from baseline will be presented by treatment group for the maximum and minimum post-treatment values and the values at the last assessment visit.

9.5.3. Pharmacokinetics Analysis

PK analysis and statistical analysis of PK endpoints will be conducted in accordance with the protocol, SAP, and the Daiichi Sankyo Analysis Guidelines. Plasma concentrations of DS-7011a will be determined using a validated analytical procedure. Specifics of the analytical method will be provided in a separate SAP.

9.5.3.1. Pharmacokinetic Parameters

Key PK parameters for DS-7011a collected from the study will be analyzed by non-linear mixed-effect modeling. Results from the analysis will be reported separately. Other parameters may be calculated, as appropriate, upon review of the data. The estimated PK parameters will be calculated for each study participant using the actual sample collection times recorded during the study.

The following PK parameters will be estimated.

PK Parameter	Definition
C _{max}	Maximum plasma concentration

PK Parameter	Definition
C_{min}	Minimum plasma concentration
AUC_t	Area under the plasma concentration-time curve up to time t, calculated by linear trapezoidal method when concentrations are increasing and by logarithmic trapezoidal method when concentrations are decreasing (Linear Up/Log Down Trapezoidal Method)
$t_{1/2}$	Terminal elimination half-life, where $t_{1/2} = (\ln 2)/K_{el}$
CL	Total body clearance, where $CL = \text{Dose}/AUC_{inf}$
V_{ss}	Volume of distribution at steady state, where $V_{ss} = CL * MRT$ (IV only), where MRT is the mean residence time of drug in plasma

9.5.3.2. Statistical Analysis of Pharmacokinetic Endpoints

PK parameters (with the exception of T_{max}) will be summarized by treatment arm using the following descriptive statistics: sample size, arithmetic mean, standard deviation (SD), coefficient of variation, minimum, median, maximum, and geometric mean. For T_{max} , the following descriptive statistics will be provided: sample size, minimum, median, and maximum.

Plasma concentrations of DS-7011a will be listed for each subject and time point and summarized with number of subjects, the number of non-missing observations (n), arithmetic mean, SD, coefficient of variation (CV%, calculated by $SD/\text{mean} \times 100$), median, minimum, and maximum values for each nominal sampling time. Similarly, plasma concentrations of DS-7011a will be summarized by ADA status.

Mean plasma concentration versus nominal time profiles will be presented for each dose level on both linear and semilogarithmic scales. Individual plasma concentration versus actual time profiles will be grouped by dose level and presented on both linear and semilogarithmic scales. Mean plasma concentrations of DS-7011a will be similarly presented by ADA status.

Additionally, scatterplots of plasma concentrations of DS-7011a and key endpoints (eg, TLR7 GS expression, IFN-Type I GS expression, skin MxA expression, and change in CLASI-A) for this Phase 1b/2 study in subjects with SLE will be presented.

9.5.4. Immunogenicity Analysis

Immunogenicity will be assessed through characterization of the incidence and titer of ADA.

The number and percentage of subjects will be calculated for the presence or absence of ADA, defining subjects who are positive for ADA at least at 1 time point as positive and subjects who are negative for ADA at all time points as negative.

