To explore the immunogenicity of 3 doses of DS-7011a given IV q4w in subjects with SLE.	Anti-drug antibodies (ADAs) against DS-7011a as the immunogenicity endpoint.	Immunogenicity
Exploratory		
To explore the mechanistic efficacy of 3 doses of DS-7011a given IV q4w in subjects with SLE.	Several endpoints indicative of mechanistic efficacy, including, but not limited to: circulating TLR7 and IFN-Type I gene signatures (GS); skin messenger ribonucleic acid (mRNA) coding for proteins under IFN-Type I regulation, such as myxovirus resistance protein (MxA), and for markers of inflammatory cells, such as CD45; and cytokines, including IL-6.	Pharmacodynamics (PD)

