8.7.3. Immunogenicity Assessments

Blood samples will be collected and analyzed for ADAs for DS-7011a in plasma at predose on Day 1, predose on Day 29, predose on Day 57, on Day 85, and on Day 113. The ADA testing will be performed using a validated assay and will involve a tiered assessment including screening, confirmation, and titer determination. ADA samples confirmed positive will be stored for neutralizing ADA. Plasma samples will be collected on Day 169 only from subjects positive for ADA on Day 113. For subjects positive for ADA on Day 169, additional plasma ADA samples will be collected every 3 months (± 1 month) up to 1 year from Day 1, or until the subject becomes negative (or, applicable to when preexisting ADA is observed, ADA titer becomes less than baseline), or shows an ADA decrease for three consecutive visits, or withdraws consent from the study, whichever occurs first.

The blood samples will be processed and shipped according to Laboratory Processing Specifications to be provided in a Laboratory Manual.

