9.2. Sample Size Determination

The study will enroll up to 24 subjects with SLE in 2 parallel arms randomized to receive 2:1 DS-7011a or placebo. Tentatively, 9 of these 24 subjects will be of African descent. Also, tentatively, 9 of these 24 subjects will be positive for anti-Sm and/or anti-RNP autoantibodies.

The sample size selected is not based on statistical power considerations. The number of subjects in each arm is considered sufficient to achieve the objectives of this study. Initial evidence of DS-7011a efficacy will be inferred by the impact DS-7011a shows on clinical endpoints, mainly CLASI-A, and several mechanistic endpoints. This impact will be evinced by comparing endpoint values between DS-7011a-treated and placebo-treated subjects and between pretreatment (baseline) and post-treatment time points. Concomitant and consistent impact on multiple endpoints will be initial evidence of efficacy, especially if this impact is of large extent. DS-7011a extent of impact will be compared to that reported for antibodies approved (belimumab and anifrolumab) or in late phase of development (BIIB059) for the treatment of SLE². The result of this comparison will inform a DS-7011a “go/no-go” decision to further development.

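### The ADA-positive rule in Section 9.5.4 counts the predose Day 1 sample, so pre-existing reactivity enters the incidence meant to describe the immunogenicity of DS-7011a

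*Combined protocol and SAP*

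**What the plan says.** Section 3 (Table 3.1) lists the immunogenicity of three doses of DS-7011a as a secondary objective, with "Anti-drug antibodies (ADAs) against DS-7011a as the immunogenicity endpoint".

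Section 9.5.4 sets out the analysis: "Immunogenicity will be assessed through characterization of the incidence and titer of ADA". It then gives the only classification rule in the text available for review. The positive class is formed by "defining subjects who are positive for ADA at least at 1 time point as positive", and the negative class is "subjects who are negative for ADA at all time points as negative".

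Section 8.7.3 fixes the sampling: "Blood samples will be collected and analyzed for ADAs for DS-7011a in plasma at predose on Day 1", then predose on Days 29 and 57, and on Days 85 and 113. Day 169 is added for subjects positive on Day 113. Table 1.1 shows the same Day 1 sample, marked predose by footnote c. Testing is tiered: screening, confirmation and titre.

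Section 8.7.3 and footnote e of Table 1.1 mention pre-existing ADA once, among the conditions for ending the extra sampling after Day 169: "applicable to when preexisting ADA is observed, ADA titer becomes less than baseline".

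ADA status is used again in Section 9.5.3.2, where "plasma concentrations of DS-7011a will be summarized by ADA status", as are the mean concentration profiles.

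**The concern.** Antibody reactivity found before any drug has been given cannot have been caused by the drug. A rule that counts a positive result at any time point, with a pre-exposure sample among those time points, reports a mixture of pre-existing reactivity and response to treatment under one count. The stated objective concerns only the second.

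The protocol has the pieces of a better rule but does not apply them here. Section 8.7.3 compares titre with baseline to decide when sampling ends. Section 9.5.2.1 defines treatment-emergent adverse events as those that are new after the first dose, or present before it and worse afterwards. Section 9.5.4 makes neither distinction for ADA. It also does not say that the counts are split by treatment group, whereas Sections 9.5.1, 9.5.2.1 and 9.5.5 do. Unexposed placebo subjects with background reactivity could therefore enter the same numerator.

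Two outputs are affected: the reported ADA incidence, and the concentration summaries by ADA status if they use the same classification.

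**Working it through.** The plan gives no ADA rate, so there is no figure of its own to reproduce. The check has two parts.

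**1. What the rule does to each kind of subject**

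| Day 1 predose | After dosing | Section 9.5.4 | Treatment-emergent rule |
|---|---|---|---|
| Negative | Negative throughout | Negative | Negative |
| Negative | Positive at least once | Positive | Positive (induced) |
| Positive | Titre rises above baseline | Positive | Positive (boosted) |
| Positive | Titre unchanged or lower | Positive | Not treatment-emergent |
| Positive | Negative throughout | Positive | Not treatment-emergent |

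The rules differ only in the last two rows. Under Section 9.5.4 those subjects cannot be negative, because the negative class requires every time point to be negative.

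**2. Size**

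*Inputs.* Section 9.2: "The study will enroll up to 24 subjects with SLE in 2 parallel arms randomized to receive 2:1 DS-7011a or placebo". This gives 24 × 2/3 = 16 active and 24 × 1/3 = 8 placebo. Baseline ADA prevalence *b* is not in the documents. I assume 2%, 5%, 10% and 15% to show a range.

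*One subject.* 1/16 = 6.25 percentage points of active-arm incidence, and 1/8 = 12.5 points of placebo-arm incidence. With fewer than 16 active subjects the step is larger.

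*Baseline-positive subjects among 16.* The expected number is 16*b*. The chance of at least one is 1 − (1 − *b*)^16. For *b* = 5%, this is 1 − 0.95^16 = 1 − 0.440 = 0.560.

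*Effect on the reported incidence.* Let *t* be the chance of a treatment-emergent response, assumed the same whether or not the subject is positive at baseline. The written rule then has expected incidence 1 − (1 − *b*)(1 − *t*), and a treatment-emergent rule has *t*. The excess is *b*(1 − *t*), the share who are baseline positive and not boosted.

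| Assumed *b* | 16*b* | Chance of at least one baseline-positive of 16 | Written rule, *t* = 0 | Written rule, *t* = 10% | Excess at *t* = 10% |
|---|---|---|---|---|---|
| 2% | 0.32 | 28% | 2% | 11.8% | 1.8 points |
| 5% | 0.8 | 56% | 5% | 14.5% | 4.5 points |
| 10% | 1.6 | 81% | 10% | 19.0% | 9.0 points |
| 15% | 2.4 | 93% | 15% | 23.5% | 13.5 points |

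If the drug induced no antibodies at all (*t* = 0), the written rule would still have an expected incidence equal to the baseline prevalence, where a treatment-emergent rule would have zero.

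Columns two and three count baseline-positive subjects. They equal the misclassified subjects only if none is boosted, so they are upper bounds on misclassification.

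**The case against.** The strongest reply is that little is at stake and nothing is lost. Section 9.1 says this is not a hypothesis-testing study. ADA is a descriptive secondary count, and no decision rule is attached to it: Section 9.2 rests the go/no-go on CLASI-A, other clinical endpoints and mechanistic endpoints. The Day 1 sample and the titres are collected, and Section 9.5.4 covers titre as well as incidence, so a baseline-adjusted split could be made later. Section 9.5 says the SAP will be finalised before database lock, and Section 10.1.1 allows changes to the planned analysis to be documented there.

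All of that is true, and it lowers the severity. It does not remove the defect. Section 9.5.4 states a rule, and that rule gives the wrong count for the objective. The text available for review contains no SAP wording that replaces it. That a correct split is feasible is not the same as its being specified.

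A reader might infer three stronger things that the documents do not support:

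- **That the mixing hides an effect of ADA on clearance.** Section 9.5.3.2 splits concentrations, not clearance. It also calls for individual concentration profiles and subject listings, and Section 9.5.3.1 estimates clearance by a separately reported model. Nor does it say that ADA status there means the class in Section 9.5.4. Pre-existing antibodies might themselves alter exposure, so the direction is unknown. Mixing could blur a difference in concentrations; no more than that follows.
- **That the protocol predicts pre-existing ADA.** Section 8.7.3 only provides for the case in which it is observed.
- **That 28% to 93% is the chance of a misclassified subject.** It is the chance of a baseline-positive one, at assumed prevalences.

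**Conclusion.** The rule is wrong as written and should be fixed, though it does not threaten the study. It counts pre-existing reactivity as ADA positivity in an endpoint meant to describe the immunogenicity of DS-7011a.

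The firm figure is 6.25 percentage points of active-arm incidence for each baseline-positive, unboosted subject, given 16 active subjects. How many there will be cannot be known from the documents. The range in the working rests on assumed prevalences of 2% to 15% and on independence between subjects; the incidence columns also assume that response does not depend on baseline status. What the final report will show is likewise open until the SAP is written, so the conclusion applies to the rule now in Section 9.5.4.

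**What to change.** Amend Section 9.5.4, and carry the same text into the SAP before database lock:

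1. Tabulate baseline (predose Day 1) ADA prevalence on its own.
2. Define treatment-emergent ADA as either negative at predose Day 1 and positive at any later sample (induced), or positive at predose Day 1 with a later titre above baseline by a prespecified margin (boosted). Set the margin from the assay's titre precision; the documents give no figure for it.
3. Use as denominator the subjects with a baseline sample and at least one post-dose sample.
4. Present baseline and treatment-emergent counts by treatment arm. The placebo arm then shows background reactivity directly.
5. State in Section 9.5.3.2 that treatment-emergent status drives the concentration summaries and profiles by ADA status.

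The cost is one paragraph and slightly more tabulation. No new samples or assays are needed, because the Day 1 sample and the titre tier are already planned in Section 8.7.3.

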6. STUDY DRUG(S)

6.1. Study Drug(s) Description

Table 6.1 describes the formulation, dose, regimen, duration, packaging, and labeling of the study drug and placebo.

Table 6.1: Study Drug Dosing Information

Study Drug Name	DS-7011a
Dosage Formulation	Provided as sterile solution in vials of 2 mL at a concentration of 100 mg/mL
Dosage Level	20 mg/kg
Route of Administration	Intravenous
Dosing	Intravenous infusions over 1 hour once every 4 weeks on Day 1, Day 29, and Day 57
Duration	Once every 4 weeks for 8 weeks (Weeks 0, 4, and 8)
Packaging	Glass vials/carton Packaging will clearly display the name of product, storage condition, and other required information as applicable in accordance with local regulations.
Labeling	Vials will be labeled as required per local regulatory requirement.
Source	DS-7011a will be supplied by the Sponsor.

DS-7011a will be provided as a sterile solution in vials of 2 mL at a concentration of 100 mg/mL and will be infused diluted in dextrose 5% in water (D5W). Placebo will be prepared using D5W or normal saline as a possible alternative. DS-7011a and placebo will be administered by IV infusion. DS-7011a will be given at the dose of 20 mg/kg q4w IV. The DS-7011a dose was selected based on the safety, tolerability, PK, and PD results of the DS-7011a FIH Phase 1a study. The intent is to select the optimal dose that is found in Phase 1a to be safe, well tolerated, and maximally active pharmacodynamically.

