8.7. Pharmacokinetic, Pharmacodynamic, Pharmacogenetic, and Immunogenicity Assessments

8.7.1. Pharmacokinetic Assessment(s)

Blood samples will be collected and analyzed for DS-7011a in plasma at the following time points ([Table 8.1](#)).

Table 8.1: Schedule of Blood Collection Times

Sample Type	Schedule Time (hours)
Plasma	Day 1 (at predose and at end of infusion), Day 2 (24 hours after administration), Day 8 (1 week after administration), Days 29 and 57 (at predose and at end of infusion), and Days 85 and 113

Allowable time windows for PK blood samples are provided in [Section 10.5](#).

The blood samples will be processed and shipped according to Laboratory Processing Specifications.

The following key PK parameters will be derived, including but not limited to: AUC_t , C_{max} , C_{min} , $t_{1/2}$, CL, and V_{ss} .

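### Section 9.5.4 counts a subject as ADA negative whatever the drug level in the sample; if the assay's drug tolerance is low, some of those negatives cannot be interpreted

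*Combined protocol and SAP*

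**What the plan says.** Immunogenicity is a secondary objective, and ADA is its only endpoint (Table 3.1). Section 9.5.4 states: "The number and percentage of subjects will be calculated for the presence or absence of ADA". One positive time point makes a subject positive, and the section classes "subjects who are negative for ADA at all time points as negative".

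Section 8.7.3 takes ADA samples at "predose on Day 1, predose on Day 29, predose on Day 57, on Day 85, and on Day 113". It adds: "Plasma samples will be collected on Day 169 only from subjects positive for ADA on Day 113". The testing uses a "validated assay and will involve a tiered assessment including screening, confirmation, and titer determination". No drug tolerance is stated.

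Table 6.1 gives the dosing as "Intravenous infusions over 1 hour once every 4 weeks on Day 1, Day 29, and Day 57". Section 8.7.1 schedules PK samples on Days 1, 2 and 8 and then on "Days 29 and 57 (at predose and at end of infusion), and Days 85 and 113", so each ADA sample up to Day 113 has a concentration from the same visit. Section 9.5.3.2 says that "plasma concentrations of DS-7011a will be summarized by ADA status". Nowhere does the concentration qualify a negative ADA result.

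**The concern.** Circulating drug can mask anti-drug antibody in an assay. A negative sample is evidence of absence only if the drug level in it is one the assay tolerates. The rule in 9.5.4 does not ask. The sampling scheme adds to this: the sample with least drug, Day 169, is not taken from subjects who are negative on Day 113, so a subject masked up to then is not tested again and is counted under absence of ADA.

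Two results would suffer if tolerance is low. First, ADA incidence would be understated, and only in the DS-7011a arm, because placebo subjects carry no drug. Second, in the 9.5.3.2 summary, masking would move high-concentration subjects into the negative group. True ADA-driven clearance gives the same pattern (higher concentrations in negatives than in positives), so the planned table could not tell the two apart.

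**Working it through.** The protocol gives no figure for ADA rate, assay tolerance or half-life, so there is nothing of its own to reproduce. The check asks how much drug to expect at each ADA visit, and what that implies over a range of tolerances.

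**Inputs.** After a single 20 mg/kg dose in healthy subjects, Cmax = 719 ug/mL and AUCinf = 8838 day*ug/mL (sections 2.3 and 4.3). Doses are on Days 1, 29 and 57. Days since each dose already given: Day 29: 28; Day 57: 56, 28; Day 85: 84, 56, 28; Day 113: 112, 84, 56; Day 169: 168, 140, 112.

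**Step 1, one compartment.** k = 719/8838 = 0.0814 per day, so the half-life is ln 2/0.0814 = 8.5 days. The level is the sum of 719·exp(-kt) over doses given. For Day 29: 719·exp(-0.0814 × 28) = 73.7.

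**Step 2, two compartments.** C(t) = A·exp(-at) + B·exp(-bt), with A + B = 719 and A/a + B/b = 8838, so B = (8838 - 719/a)/(1/b - 1/a). Assumed distribution half-life 1 day (a = 0.693). For an assumed terminal half-life of 14 days (b = 0.0495), B = 416 and A = 303. For 21 days (b = 0.0330), B = 270 and A = 449.

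| Expected ug/mL | Day 29 | Day 57 | Day 85 | Day 113 | Day 169 |
|---|---|---|---|---|---|
| One compartment | 73.7 | 81.3 | 82.0 | 8.4 | 0.09 |
| Terminal 14 d | 104 | 130 | 136 | 34 | 2.1 |
| Terminal 21 d | 107 | 150 | 167 | 66 | 10.4 |

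**Step 3, subject level.** One positive sample makes a subject positive, so a negative subject is wholly uninterpretable only if all four post-dose samples exceed the tolerance T. Assume a lognormal subject multiplier on the whole curve, with mean 1 and CV 30%: σ = √ln(1.09) = 0.2936. Day 113 is the lowest of the four, so

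share = 1 - Φ([ln(T/C113) + σ²/2]/σ), with σ²/2 = 0.043.

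- One compartment, T = 10: (0.173 + 0.043)/0.2936 = 0.74, share 23%.
- Terminal 21 d, T = 50: (-0.280 + 0.043)/0.2936 = -0.81, share 79%.
- Terminal 21 d, T = 100: (0.413 + 0.043)/0.2936 = 1.55, share 6%.

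| T (ug/mL) | One compartment | Terminal 14 d | Terminal 21 d |
|---|---|---|---|
| 10 | 23% | 100% | 100% |
| 50 | 0% | 7% | 79% |
| 100 | 0% | 0% | 6% |
| 200 | 0% | 0% | 0% |

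**Sensitivity.** If the modelled level is taken as the median and not the mean (dropping the 0.043), 23%, 79% and 6% become 28%, 83% and 8%. With an assumed terminal half-life of 28 days, Day 113 is 87.6 ug/mL and the share at T = 100 is 28%: (0.132 + 0.043)/0.2936 = 0.60.

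**Step 4, in subjects.** Full enrolment gives 24 × 2/3 = 16 on DS-7011a, so each subject is worth 1/16 = 6.25 points of incidence. Shares of 23%, 79% and 6% are about 3.7, 12.6 and 1.0 subjects.

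**Step 5, effect on the report.** Suppose no subject is positive and four are inconclusive. The current rule reports 0/16, exact 95% upper limit 1 - 0.025^(1/16) = 20.6%. The qualified rule reports 0/12, upper limit 1 - 0.025^(1/12) = 26.5%, with four inconclusive beside it.

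**The case against.** Three stronger readings are tempting, and the documents do not support them.

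- A reader might infer that all post-dose samples carry high drug levels. Day 113 is 56 days after the last dose, section 4.1.1 expects exposure to have fallen by then, and the one-compartment value of 8.4 ug/mL is about 1% of Cmax. What can be said is that drug is expected to be present.
- A reader might infer that incidence is biased downward. That depends on a tolerance that the documents do not give. At 200 ug/mL essentially no subject is wholly uninterpretable.
- A reader might take the share of samples above tolerance as a miss rate. With a 21-day half-life and T = 100, the shares on Days 29, 57, 85 and 113 are 54%, 89%, 95% and 6%. They average 61% of samples, but only 6% of subjects lack an interpretable sample. Even an uninterpretable negative is a miss only if antibody was there, and no ADA prevalence is available. Conversely, transient antibody at a masked early visit can be missed when Day 113 is interpretable; that is not quantified here.

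It can also be said that section 9.5 leaves detail to a SAP finalised before database lock, that the assay is validated, and that individual concentrations will be listed, so negatives could be matched by hand. This shows an opportunity to handle the matter, not that it is handled: 9.5.4 is the only classification rule in the text. Finally, the study is exploratory, ADA is descriptive, and section 9.2 rests go/no-go on clinical and mechanistic endpoints. That limits the consequence and stands.

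**Conclusion.** The point holds as a conditional weakness in a stated rule. A negative in 9.5.4 is not qualified by drug level, drug is expected at every post-dose ADA sample taken from all subjects, and the lower-drug Day 169 sample is withheld from Day 113 negatives. Whether this matters turns on one unknown. Subjects with no interpretable post-dose sample run from about 23-100% at a tolerance of 10 ug/mL to 0-80% at 50, 0-6% at 100 and 0% at 200. Masking itself is not demonstrated.

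The sizes rest on single-dose PK from healthy subjects, linear kinetics, assumed terminal half-lives up to 21 days and an assumed 30% CV. Only the one-compartment case needs no assumed half-life, and it gives the low end of each range. A half-life longer than 21 days would raise the upper ends.

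**What to change.** State the assay's validated drug tolerance in the SAP and change 9.5.4 as follows.

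- A positive sample stays positive under the existing rule.
- A post-dose sample is negative only if the DS-7011a concentration at the same visit is at or below the tolerance; otherwise it is inconclusive. On Days 29 and 57 use the predose concentration, not the end-of-infusion one. Placebo samples contain no drug and are conclusive.
- A subject is positive (any positive), negative (no positive and the last sample conclusive) or inconclusive.
- Report incidence among evaluable subjects (positive plus negative), with the inconclusive count beside it.
- Use the same three classes for the concentration summaries and plots in 9.5.3.2.

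The cost is SAP wording and one merge of ADA with PK data already collected; no visit or sample is added. If tolerance proves high, almost nobody is reclassified and the negatives are better supported. The downside is that some subjects now counted as negative become inconclusive, in an arm of about 16. Relabelling also does not recover masked antibody: that would need a low-drug sample, such as Day 169, from Day 113 negatives, which is a schedule change and not part of this proposal.
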